10. CONDUCT OF STUDY

The investigational site is to maintain complete documentation of all events and the times at which they occur.

10.1 Completion of Study

The investigational site will complete the study and complete all documentation required, in satisfactory compliance with the protocol, within 3.5 months of enrollment of the last subject and extending beyond as needed to complete necessary data queries.

It is agreed that, for reasonable cause, either the investigator or Perrigo may terminate this study before completion provided written notice is submitted at a reasonable time in advance of intended termination. Any extension of this study must be mutually agreed upon in writing by both the investigator and Perrigo.

10.2 Protocol Amendments

The Investigator will not make any changes to this protocol without prior written consent from Perrigo and subsequent approval by the IRB. Any permanent change to the protocol, whether it is an overall change or a change for specific study center(s), must be handled as a protocol amendment. Any amendment to the protocol that appears indicated as the study progresses will be fully discussed between [REDACTED] and Perrigo. If agreement is reached regarding the need for an amendment, the amendment will be written by Perrigo. The written amendment must be submitted to the chairman of the IRB identified with this responsibility. Except for 'administrative amendments', investigators must await IRB approval of protocol amendments before implementing the change(s). Administrative amendments are defined to have no effect on the safety of the research subjects, scope of the investigation, or quality of the trial. However, a

protocol change intended to eliminate an apparent immediate hazard to subjects should be implemented immediately, and the IRB notified within five days. Perrigo will submit protocol amendments to the FDA or other regulatory agencies.

When, in the judgment of the reviewing IRB, the investigators and/or Perrigo, the amendment to the protocol substantially alters the study design and/or increases the potential risk to the subject, the currently approved written informed consent form will require similar modification. In such cases, repeat informed consent will be obtained from subjects enrolled in the study before expecting continued participation.

11. RECORDS MANAGEMENT

11.1 Data Collection

CRFs for individual subjects will be provided [REDACTED]. CRFs must be legible and complete. CRFs for this study will be maintained in a study binder and data recorded on 2-part NCR paper. One copy will be kept by the investigator and the other copy will be submitted to the CRO data management group. All forms should be completed using a black ballpoint pen. Errors should be lined out, *but not obliterated*, and the correction inserted, initialed, and dated by designated study personnel. Further data corrections will be performed on data correction forms (DCFs) that will be provided by the CRO to the investigator in case of erroneous or unclear data. The investigator will make the correction on the DCF and sign the DCF. The signed DCF will be submitted to the CRO data management group for processing and a copy retained with the CRFs.

A CRF must be completed and signed by the investigator for each subject enrolled, including those discontinued from the study for any reason. The reason for discontinuation must be noted on a subject's study termination form.

CRFs must be kept current to reflect the subject's status at each phase during the course of the study. Subjects are not to be identified on CRFs by name; appropriately coded identification and the subject's initials must be used. The investigator must keep a separate log of the subjects' names and addresses.

During each subject's visit to the clinic, a designee participating in the study will record progress notes to document all significant observations. At a minimum, these notes will contain:

- a) Documentation of the informed consent process;
- b) The date of the visit and the corresponding Visit or Week in the study schedule;
- c) General subject status remarks, including any significant medical findings. The severity, frequency, and duration of any adverse events and the investigator's assessment of relationship to study medication must also be recorded.
- d) Any changes in concomitant medications or dosages;
- e) A general reference to the procedures completed; and
- f) The signature (or initials) and date of all clinicians who made an entry in the progress notes.

In addition, any contact with the subject via telephone or other means that provides significant clinical information will also be documented in the progress notes as described above.

Any changes to information in the study progress notes and other source documents, will be entered in **black ink, initialed and dated** by the authorized person making the correction/addition. Changes will be made by striking a single line through erroneous data, and clearly entering the correct data. (e.g., ~~wrong data~~ right data). Entries may not be erased or masked with white-out fluid. If the reason for the change is not apparent, a brief explanation for the change will be written adjacent to the change by the clinician.

For transmission to Perrigo, information from the study progress notes and other source documents will be promptly entered into the database. The database also contains a complete audit trail to capture all regulatory components of data corrections (e.g. initial entry, new value, initials and date of the change).

11.2 Source Documents

Source documents are defined as the results of original observations and activities of a clinical investigation. Source documents will include, but are not limited to, progress notes and screening logs. All source documents pertaining to this study will be maintained by the investigators and made available for inspection by authorized persons. The original signed informed consent form for each participating subject shall be filed with records kept by the investigators and a copy given to the subject.

11.3 File Management at the Study Site

It is the responsibility of the investigator to ensure that the study center file is maintained in accordance with Section 8 of the International Conference on Harmonization (ICH) Guideline for Good Clinical Practices (GCP).

11.4 Records Retention at the Study Site

FDA regulations require all investigators participating in clinical drug studies to maintain detailed clinical data for one of the following periods:

- a) A period of at least two years following the date on which a New Drug Application is approved by the FDA;
- b) A period of two years after Perrigo
- c) notifies the investigator that no further application is to be filed with the FDA.

The investigator must not dispose of any records relevant to this study without either (1) written permission from Perrigo or (2) providing an opportunity for Perrigo to collect such records. The investigator shall take responsibility for maintaining adequate and accurate electronic or hard copy source documents of all observations and data generated during this study, including any data correction forms (DCFs) received from Symbio, LLC. Such documentation is subject to inspection by Perrigo and the FDA.

12. QUALITY CONTROL AND QUALITY ASSURANCE

12.1 Monitoring

Protocol No: PRG-NY-15-003

Perrigo has ethical, legal and scientific obligations to carefully follow this study in a detailed and orderly manner in accordance with established research principles and FDA regulations. All medical records (source documents) of the subjects participating in this study must be presented for review and verification of CRFs.

12.2 Auditing

Perrigo (or representative) may conduct audits at the study center(s). Audits will include, but are not be limited to, drug supply, presence of required documents, the informed consent process, and comparison of case report forms with source documents. The investigator agrees to participate with audits conducted at a reasonable time in a reasonable manner.

Regulatory authorities worldwide may also audit the investigator during or after the study. The investigator should contact Perrigo immediately if notified of such an audit, and must fully cooperate with the audits conducted at a reasonable time in a reasonable manner.

13. ETHICS AND RESPONSIBILITY

This study must be conducted in compliance with the protocol, the United States Food and Drug Administration (FDA) regulations, any other countries regulations, and ICH GCP Guidelines.

1 Purpose of Statistical Analysis Plan

The purpose of the statistical analysis plan is to describe in detail all the data, statistical methods, and [summary tables](#) required to implement the statistical analysis of Clinical Study Protocol PRG-NY-15-003 [REDACTED]

2 Study Objectives

To compare the safety and efficacy profiles of Perrigo UK FINCO Clindamycin Phosphate and Benzoyl Peroxide Topical Gel 1.2%/3.75% to Valeant Pharmaceuticals Onexton™ Topical Gel (Clindamycin Phosphate and Benzoyl Peroxide Gel 1.2%/3.75%) and to demonstrate the superior efficacy of the two active formulations over that of the vehicle in the treatment of acne vulgaris.

3 Study Design

For the purpose of exploring the above objectives, the study will be conducted as a double-blind, randomized, parallel-group, vehicle-controlled, multicenter trial.

[figure not shown]
Approximately [REDACTED] healthy males and females, 12 to 40 years of age, inclusive, who meet the inclusion/exclusion criteria, will be enrolled to obtain approximately [REDACTED] modified-Intent-To-Treat (mITT) and [REDACTED] per-protocol (PP) subjects. [REDACTED]

The actual number of subjects enrolled in the study will be based on blinded review of subject status (related to the per-protocol definition, [section 4](#)) to determine that the number of subjects expected to meet the PP criteria is sufficient [REDACTED]. If this number is expected to be met prior to enrolling [REDACTED] subjects, the enrollment will be closed.

Each subject will be randomly assigned to one of following treatment groups in a [REDACTED] ratio:

- (1) Test: Clindamycin Phosphate and Benzoyl Peroxide Topical Gel 1.2%/3.75%, [REDACTED]

(2) Reference: Onexton™ Topical Gel (Clindamycin Phosphate and Benzoyl Peroxide Gel 1.2%/3.75%), Valeant Pharmaceuticals North America, LLC
(3) Vehicle of test product Perrigo UK FINCO, [REDACTED]

Subjects will be admitted into the study only after written informed consent has been obtained and all of the inclusion and none of the exclusion criteria have been met. Randomization will be performed according to a computer generated randomization scheme where the treatment group designation has been assigned to the subject number. The treatment designation will remain blinded until the final database is closed. An independent third party generator will generate and hold the randomization code throughout the study. Randomized subjects will apply [REDACTED] study medication onto six areas of the face (chin, left cheek, right cheek, nose, left forehead and right forehead) [REDACTED] avoiding contact with the eyes, lips, mouth, broken areas of the skin and mucous membranes at approximately the same time once daily for 12 weeks.

Subjects will be scheduled for an office visit for Visit 1/Day 1 (Baseline), Visit 2/Week 4/Day 28 (± 4 days)(Interim, Visit 3/Week 8/Day 56 (± 4 days)(Interim), and Visit 4/Week 12/Day 84 (± 4 days) (End of treatment/End of study). Safety will be assessed by monitoring adverse events at each visit and at the Week 2/Day 15 (± 4 days) Telephone Contact.

4 Populations To Be Analyzed

Three subject populations are defined as follows:

- (1) Intent-to-Treat (ITT) (safety population): Any subject that was randomized, received and used study medication;
- (2) Modified Intent-to-Treat (mITT): Any subject, who met the inclusion/exclusion criteria, was randomized, received and used the study medication, and returned for at least one post-baseline efficacy assessment;
- (3) Per-Protocol (PP): Any subject:
 - Who met inclusion/exclusion criteria,
 - Who was randomized and received and used study medication,
 - Who met the protocol criteria for compliance [REDACTED]
[REDACTED]
and
[REDACTED]
 - Who completed Visit 4/Week 12/Day 84 (End of Treatment/Early Termination Visit) within window OR was dropped from the study due to treatment failure [REDACTED]
[REDACTED] treatment [REDACTED]
 - Without significant protocol violations that could have interfered with the administration of the treatment or the precise evaluation of treatment efficacy.

[REDACTED]

[REDACTED]

5 Planned Analyses

5.1 Methodological Considerations

The study will be conducted under the same protocol across all the sites. No formal statistical analyses are planned to evaluate the consistency of efficacy results across the multiple clinical sites. These results, however, will be tabulated and if a site's efficacy data are obviously inconsistent with the results across all sites, this will be explored and addressed in the final study report.

Two-sided hypothesis testing will be conducted for all the tests. Resulting p-values less than 0.05 will be considered statistically significant unless noted otherwise. No adjustments of p-values for multiple comparisons will be made. No interim analyses are planned. SAS software will be used for all data analyses and tabulations.

5.2

[REDACTED]

[REDACTED]

5.3 Demographics and Baseline Characteristics

Baseline variables (e.g., sex, age, ethnic origin) will be evaluated, adjusting for site, to identify differences between treatment groups, which were not eliminated by randomization. Any significant baseline differences will be reviewed for their potential impact on the efficacy findings.

Continuous variables at baseline will be examined by two-way analysis of variance (ANOVA) with treatment and site as fixed effects when normal error and homogeneous variance assumptions are satisfied, or by the nonparametric rank based ANOVA when they are not, to compare treatment group differences.

Categorical variables such as gender, race, etc., will be examined by Cochran-Mantel-Haenszel test, stratified by site.

Summary tables by treatment group will be presented. For each continuous variable, the summary will include the mean, standard deviation, minimum and maximum. For each categorical variable, the summary will include frequencies and percentages.

5.4 Subject Accountability

A summary of subject disposition will be provided for all subjects. Descriptive summaries of subject disposition, reason for discontinuation, and analyses population will be provided by treatment group. The data will also be presented in **subject data listings**.

5.5 Efficacy Variables and Analyses

5.5.1 Primary Endpoints

The primary efficacy endpoints are the mean percent change from baseline to Week 12 (Visit 4/Day 84) in the inflammatory (papules and pustules) lesion counts AND the mean percent change from baseline to Week 12 (Visit 4/Day 84) in the non-inflammatory (open and closed) lesion counts.

Equivalent Efficacy

For the mean percent change from baseline in the inflammatory lesion counts, the Test treatment will be considered to be therapeutically equivalent to the Reference treatment if the 90% confidence interval on the Test-to-Reference ratio of means, calculated by Fieller's Method, falls within the interval 0.80 to 1.25. The compound hypothesis to be tested for therapeutic equivalence between test and reference is:

$$H_0: \mu_T / \mu_R \leq 0.80 \text{ or } \mu_T / \mu_R \geq 1.25 \text{ versus}$$

$$H_A: 0.80 < \mu_T / \mu_R < 1.25.$$

Where μ_T and μ_R are the mean percent change from baseline to Week 12 (Visit 4/Day 84) in inflammatory lesions counts for the test treatment and the reference treatments, respectively. The null hypothesis is rejected when the two-sided 90% confidence interval (CI) for the ratio of means between test and reference products is between 0.80 and 1.25. Rejection of the null hypothesis supports the conclusion of therapeutic equivalence between test and reference products for the primary efficacy variable.

The two-sided 90% confidence interval will be constructed using an ANOVA model adjusting for the effects of treatment and site.

The same analysis will be applied to the mean percent change from baseline in the non-inflammatory lesion count.

Therapeutic equivalence evaluations in the per-protocol (PP) population will be considered definitive and those in the mITT will be considered supportive.

Superiority

For the percent change from baseline in the inflammatory lesion counts, each active treatment will be evaluated to determine if it has superior efficacy to that of the Vehicle at Week 12 (Visit 4/Day 84) via ANOVA model containing terms for treatment and site. The compound hypothesis to be tested for superiority of test and reference over Vehicle is:

$$H_0: \mu_T \leq \mu_V \text{ or } \mu_R \leq \mu_V \text{ versus}$$

$$H_A: \mu_T > \mu_V \text{ and } \mu_R > \mu_V$$

Where μ_T , μ_R and μ_V are the mean percent change from baseline to Week 12 (Visit 4/Day 84) in inflammatory lesions counts for the test, the reference and the vehicle treatments, respectively. The null hypothesis is rejected when both p-values from the ANOVA are less than 0.05 (two-sided test). Rejection of the null hypothesis supports the conclusion of superiority of test and reference products over the vehicle product for the primary efficacy variable.

[REDACTED]

[REDACTED]

[REDACTED]

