5.9.1 Inflammatory Lesion Count

The numbers of facial papules and pustules, located above the jaw line to the hairline including those present on the nose, are to be counted at baseline and at each subsequent visit. The type and number of each lesion is to be recorded on the source document at each visit and the total count recorded.

Papule = solid palpable inflammatory lesion \leq 5mm diameter

Pustule = pus-filled inflammatory lesion \leq 5mm in diameter

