6.2.4 Randomization

Randomization will be performed according to a computer generated randomization scheme where the treatment group designation has been assigned to the subject number. The treatment designation will remain blinded until the final database is closed. An independent third party will hold the randomization code throughout the study. The randomization scheme will be a block randomization, with each block of seven subjects assigned to Test: Reference: Vehicle [REDACTED]
[REDACTED]

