8.1.3 Sample Size Considerations

8.1.4 Efficacy Measures and Analysis

Clinical endpoints

The primary efficacy measure will be the mean percent change from baseline to Week 12 in the inflammatory (papules and pustules) lesion counts AND the mean percent change from baseline to Week 12 in the non-inflammatory (open and closed) lesion counts. The secondary efficacy measure will be the proportion of subjects with clinical success on the Investigator's Global Assessment (IGA) at Week 12. Success is defined as an IGA score that is at least 2 grades less than the baseline assessment.

Equivalent efficacy

Protocol No: PRG-NY-15-003

For the mean percent reduction from baseline in the inflammatory and non-inflammatory lesion counts, the Test treatment will be considered to be therapeutically equivalent to the Reference treatment if the 90% confidence interval on the Test-to-Reference ratio of means, calculated by Fieller's Method, falls within the interval 0.80 to 1.25. The treatment means and estimate of residual variance for the confidence interval calculation will come from an Analysis of Variance of the Test and Reference results using a statistical model containing terms for Treatment and Site.

For the proportion of subjects with clinical success, the Test treatment will be considered to be therapeutically equivalent to the Reference treatment if the 90% confidence interval on the difference between Test and the Reference proportions is contained within the interval -20% to +20%. The confidence interval will be constructed using Wald's method with Yates' continuity correction.

Therapeutic equivalent evaluations in the per-protocol (PP) population will be considered definitive and those in the mITT will be considered supportive.

Superiority

For the percent reductions from baseline in the inflammatory and non-inflammatory lesion counts, each active treatment will be evaluated to determine if it has superior efficacy to that of the Vehicle at Visit 4/Week 12 via an Analysis of Variance using a statistical model containing terms for Treatment and Site.

The proportion of subjects with clinical success for each active treatment will be compared to that of the Vehicle using a Z-test with Yates' continuity correction.

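### Adding the matching baseline lesion count to the co-primary models would be a nearly free improvement on the treatment-and-site ANOVA

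*SAP*

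**What the plan says.** SAP 5.5.1 sets the equivalence model for the inflammatory count: "The two-sided 90% confidence interval will be constructed using an ANOVA model adjusting for the effects of treatment and site". It applies the same analysis to the non-inflammatory count. Protocol 8.1.4 takes the means and residual variance for Fieller's method from an ANOVA "using a statistical model containing terms for Treatment and Site". Superiority over vehicle is tested "via ANOVA model containing terms for treatment and site". Equivalence requires the 90% interval for the Test-to-Reference ratio to lie within 0.80 to 1.25 for each lesion type.

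The covariate is already collected. Protocol 5.9.1 says inflammatory lesions "are to be counted at baseline and at each subsequent visit", and 5.9.2 says the same for comedones.

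The only visible handling of baseline imbalance is in SAP 5.3: "Continuous variables at baseline will be examined by two-way analysis of variance (ANOVA) with treatment and site as fixed effects" (with a rank-based alternative), followed by "Any significant baseline differences will be reviewed for their potential impact on the efficacy findings". The general threshold, in SAP 5.1, is "Resulting p-values less than 0.05 will be considered statistically significant unless noted otherwise".

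Parts of SAP 5.2, 5.5.1 and 5.5.3 are redacted, and the start of the SAP table list is not available. A supplementary baseline-adjusted analysis, or tables of baseline lesion counts, may exist there.

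**The concern.** Dividing by the baseline count does not guarantee that percent change is uncorrelated with it. If a within-arm, within-site correlation r remains, omitting baseline has two effects. The residual variance is larger by a factor of about 1/(1 − r²). Also, whatever chance baseline difference this trial happens to have moves the estimated ratio, in either direction.

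An imbalance in Test's favour makes a product at the 0.80 limit more likely to pass. One against Test makes a truly similar product more likely to fail. These mirror cases offset over hypothetical repetitions, so average error stays near 5%, but the trial is run once and has one imbalance.

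The SAP 5.3 review does not fill the gap. It may well cover lesion counts, but it states no consequence for the deciding interval. It also cannot act on a non-significant imbalance, and a one-standard-error difference is non-significant. Any adjustment chosen after that review would not be prespecified.

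**Working it through.** **Inputs.** The margin, the 90% Fieller interval and the models come from SAP 5.5.1 and Protocol 8.1.4. The visible text gives no sample size, SD, expected mean or r, so there is no plan figure to reproduce. Assumed for illustration: n = 200 per-protocol subjects per active arm, reference mean 52, SD 40, 20 equal sites with site in both models, and r = 0, 0.1, 0.2, 0.3.

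**Step 1: precision.** Adjustment multiplies the residual SD, and approximately the interval width, by √(1 − r²): 0.995, 0.980 and 0.954 at r = 0.1, 0.2 and 0.3. That is equivalent to saving r² of the sample: 1%, 4% and 9%.

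**Step 2: shift from a chance imbalance.** The standard error of the baseline difference, in SD units, is √(2/200) = 0.10. An imbalance of that size moves the unadjusted Test − Reference difference by r × 40 × 0.10 = 0.4, 0.8 or 1.2 percentage points. Divided by 52, this is about 0.008, 0.015 or 0.023 on the ratio. An imbalance at least this large occurs in about 16% of randomisations in each direction.

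**Step 3: false equivalence at a true ratio of 0.80, large-sample check.** The lower-limit statistic is Test mean − 0.8 × Reference mean. Its correlation with the baseline difference is c = r × (1 + 0.8)/√(2 × 1.64). At r = 0.3, c = 0.298 and √(1 − c²) = 0.9545. Given a one-standard-error imbalance:

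- favouring Test: P(Z > (1.645 − 0.298)/0.9545) = P(Z > 1.411) = 7.9%
- against Test: P(Z > (1.645 + 0.298)/0.9545) = P(Z > 2.036) = 2.1%

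The same formula gives 7.0% and 3.0% at r = 0.2, and 6.0% and 4.0% at r = 0.1.

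**Step 4: simulation.** Subject-level simulation used 40,000 trials per cell. The ANCOVA Fieller interval included the covariance of the adjusted means. Power is for 50 versus 52; the imbalance rows are for one standard error.

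| | r = 0 | 0.1 | 0.2 | 0.3 |
|---|---|---|---|---|
| False equivalence, ANOVA, average | 4.8% | 5.0% | 5.0% | 5.0% |
| ANOVA, imbalance favours Test | 4.8% | 6.0% | 6.9% | 7.7% |
| ANOVA, imbalance against Test | 4.8% | 4.0% | 3.0% | 2.1% |
| Average power, ANOVA | 70.4% | 69.5% | 70.3% | 69.5% |
| Average power, ANCOVA | 70.2% | 69.9% | 72.0% | 73.9% |
| Power, ANOVA, imbalance favours Test | 70.2% | 72.3% | 74.6% | 76.7% |
| Power, ANOVA, imbalance against Test | 70.0% | 67.4% | 66.0% | 63.2% |

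With ANCOVA and the same one-standard-error imbalances, false equivalence is 4.8–5.1% and power about 70, 70, 72 and 75%. Repeat simulations of the r = 0.3 case agreed within simulation error (7.9% and 2.1% unadjusted; average power 70.0% versus about 74.6%).

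An edge case is r = 0.3 with a 1.95-standard-error imbalance, which occurs in about 2.6% of randomisations in each direction. Unadjusted false equivalence is then 13.1% or 0.9%, and power 78.0% or 53.2%. With ANCOVA they stay at 5.0–5.1% and 74.2–74.5%.

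**Step 5: other assumptions.** At 400 per arm, r = 0.3 and one standard error, unadjusted false equivalence is 7.8% or 2.1% and power 97.6% or 92.0%, versus 5.1–5.2% and 96.2–96.5% adjusted. With mean 55, SD 45, a true ratio of 1 and r = 0.3, approximate power goes from 90.3% to 93.1% at 300 per arm and from 51% to 58% at 150 per arm.

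**Step 6: how large might r be?** A skewed-count check used lognormal baselines, an assumed entry threshold of 20 lesions and Poisson Week 12 counts. Baseline fluctuation of 0, 10, 20 and 30% CV alone gave r of about 0, 0.02, 0.07 and 0.13. At r = 0.13, over all imbalances of at least one standard error, unadjusted false equivalence was 7.6% favouring Test and 3.1% against. Adjustment gave 5.3% and 5.0% (linear baseline) or 5.3% and 4.9% (log baseline). At r of 0.02 or less there was no material gain. The overall rate in this check was 5.6–6.0% with or without baseline.

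**Step 7: superiority.** Protocol 6.2.4 gives a block of seven with the split redacted, so two splits were assumed. Normal-approximation power for one comparison is Φ(difference/SE − 1.96), with SE = 40 × √(1 − r²) × √(1/n₁ + 1/n₂).

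- 3:3:1 (200 versus 67), 15-point difference: SE = 5.65 at r = 0. Power is 75.7, 76.1, 77.4 and 79.5% at r = 0, 0.1, 0.2 and 0.3.
- 2:2:3 (200 versus 300), 10-point difference: SE = 3.65 at r = 0. Power is 78.2, 78.6, 79.8 and 81.9%.

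**The case against.** The strongest reply is that nothing here is wrong. The two documents agree, the ANOVA is valid under randomisation, and its average false-equivalence rate is about 5% at every r in the main simulation. Percent change already uses each subject's own baseline, and no visible text supports an r of 0.2 or 0.3. At r = 0.13 the interval narrows by only 0.85%, average power at 200 per arm rises from 70.1% to 70.9%, and a one-standard-error imbalance moves the ratio by about 0.010. The larger swings need both r = 0.3 and an unusual imbalance. Arguing from one realised imbalance would apply to any prognostic baseline variable. SAP 5.3 does look at baseline differences, and redacted text may already hold an adjusted analysis.

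Most of this stands, and it limits the point to an improvement of uncertain size. It does not remove the case for acting. The loss at r = 0 is negligible, while the gain at moderate r is useful, and r need not be known in advance.

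Two qualifications also stand. A linear term removes only the linear effect of imbalance in the matching count; it does not address other selection into the per-protocol population. And the change is not wholly free, because Protocol 10.2 treats permanent protocol changes as amendments.

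**Conclusion.** The point holds as a recommended improvement, not as an error. The visible deciding models omit a covariate that is measured in advance and matches each endpoint. The direction of the benefit and the √(1 − r²) factor are firm; the size is illustrative because sample size, SD, means, allocation and r are all assumed. For r between 0.1 and 0.3 the interval narrows by about 0.5% to 5%. A one-standard-error imbalance moves unadjusted false equivalence from about 5% to 6.0–7.7% or to 4.0–2.1%, whereas adjustment keeps it near 5%. If r is close to 0, there is little to gain and almost nothing to lose. Confidence is medium, because the redacted parts of the SAP could already contain an adjusted analysis.

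**What to change.** Before unblinding, prespecify ANCOVA with treatment, site and the matching baseline count (inflammatory for the first endpoint, non-inflammatory for the second), for both equivalence and superiority. State whether the count enters on its original or a log scale; the two performed alike in the skewed-count check. Evaluate the adjusted means at the common mean baseline, and pass them with their full covariance matrix to Fieller's method, because adjustment makes the Test and Reference means correlated. Keep the treatment-and-site ANOVA as a sensitivity analysis, and align Protocol 8.1.4 with the SAP. If redacted text already holds a baseline-adjusted analysis, state which model decides.

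The cost is wording in two documents, the amendment step under Protocol 10.2, and one degree of freedom per model. No new data are needed. If r is 0, the simulated loss of power at 200 per arm is about 0.2 points on average and at most 0.6 points, at a 1.95-standard-error imbalance. Protocol section 8 already requires the SAP to be final before the blind is broken, so the change must be made by then.

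### Could the SAP's superiority rule for lesion counts be met by an active treatment that is worse than vehicle?

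*SAP*

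**What the plan says.** The superiority part of SAP 5.5.1 opens with its aim: "each active treatment will be evaluated to determine if it has superior efficacy to that of the Vehicle at Week 12". The analysis is an ANOVA with terms for treatment and site. The null is that at least one active mean does not exceed the vehicle mean, and the alternative is "H_A: \mu_T > \mu_V \text{ and } \mu_R > \mu_V". The means are then defined as "the mean percent change from baseline to Week 12 (Visit 4/Day 84) in inflammatory lesions counts for the test, the reference and the vehicle" treatments.

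The decision rule is "The null hypothesis is rejected when both p-values from the ANOVA are less than 0.05 (two-sided test"), followed by "Rejection of the null hypothesis supports the conclusion of superiority of test and reference products over the vehicle product".

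Protocol 8.1.4 words the same test on the reduction scale: "For the percent reductions from baseline in the inflammatory and non-inflammatory lesion counts, each active treatment will be evaluated". It does so for equivalence as well: "For the mean percent reduction from baseline in the inflammatory and non-inflammatory lesion counts, the Test treatment will be considered". The opening paragraph of that section, and protocol 2.1, name the same primary measure as percent change.

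No readable passage gives a formula or a sign for percent change. SAP 5.2, the text that follows the rejection rule in 5.5.1, and SAP 5.5.3 are redacted. The table and listing shells named in the SAP's table of contents are not in the available text.

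**The concern.** There are two apparent faults in the decision rule for a primary claim.

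- **Scale.** Percent change is usually Week 12 minus baseline, divided by baseline, so improvement is negative. A better active then has the smaller mean, and the printed alternative would describe actives that are worse than vehicle.
- **Direction.** The null is one-sided, but the rejection sentence asks only for two two-sided p-values below 0.05. A significant difference in the wrong direction satisfies those words, and the next sentence treats rejection as superiority.

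Protocol section 8 makes the SAP the companion document that records the statistical evaluation, so its primary rule should not mislead. A reader who used the p-value sentence alone might accept a harmful difference as superiority. A different reader, who put signed changes into the inequality, might fail an effective product. These are alternative misreadings and do not act together.

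**Working it through.** The plan prints no figure to reproduce here: the sample size text and the allocation ratio are redacted. The check is of the logic, with arithmetic on stated assumptions.

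**1. Sign convention.** Illustrative counts (assumed): baseline 30 in each arm; Week 12 count 12 on active and 18 on vehicle.

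| | Active | Vehicle | Active − vehicle |
|---|---|---|---|
| Change, 100 × (Week 12 − baseline)/baseline | −60 | −40 | −20 |
| Reduction, 100 × (baseline − Week 12)/baseline | 60 | 40 | +20 |

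The printed inequality is true for reduction (60 > 40) and false for signed change (−60 > −40). The two variables differ only by a factor of −1. The ANOVA residual variance, the size of each difference and every two-sided p-value are therefore identical. The Test-to-Reference ratio is also unchanged, because the signs cancel: −55/−60 = 55/60 = 0.917. The label affects how the inequality reads and nothing that is computed.

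**2. The test read with its hypotheses.** A two-sided p < 0.05 with the difference in favour of the active is a one-sided test at 0.025. The null is a union (either active fails) and both comparisons must succeed, so the error for one lesion type is at most 0.025. That limit is approached when one active equals vehicle and the other is far better.

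**3. The p-value sentence used alone.** Let z for each active-minus-vehicle comparison be normal with unit variance and critical value 1.96, positive values favouring the active. The shared vehicle arm gives correlation

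ρ = (1/n_V) / √[(1/n_T + 1/n_V)(1/n_R + 1/n_V)].

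Protocol 6.2.4 gives only the block size: "The randomization scheme will be a block randomization, with each block of seven subjects assigned to Test: Reference: Vehicle". The splits of seven with equal Test and Reference are taken as assumptions: 3:3:1, 2:2:3 and 1:1:5, with ρ = 0.75, 0.40 and 0.167.

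| Truth | p-values alone | Direction required |
|---|---|---|
| One active equal to vehicle, other 6 SE better | 0.050 | 0.025 |
| One active 1 SE worse, other 6 SE better | 0.170 | 0.0015 |
| Both actives 3 SE better (3:3:1, 2:2:3, 1:1:5) | 0.79, 0.75, 0.73 | 0.79, 0.75, 0.73 |

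With no difference anywhere, the chance that both comparisons are significant against the actives is 0.0095, 0.0034 and 0.0014 for the three splits.

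The first two rows show what the words would permit if cut off from the hypotheses. In the second, 0.170 − 0.0015 = 0.1685 is the chance that the weaker active is significantly worse than vehicle. Calling that superiority would contradict the printed null and the estimates reported beside the p-value. The last row shows that power for a true benefit does not depend on whether the direction is restated.

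**4. The passages together.** The rejection sentence names the null hypothesis, and the null it names is the directional one set out immediately before it. An estimate in the wrong direction is not evidence against that null. The introductory sentence and the study objectives (SAP 2) both speak of superior efficacy. Protocol 8.1.4 names the measure as percent change and then tests it as percent reduction, so the two terms denote one variable. On that usage the SAP inequality is right as printed.

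**The case for a change.** The best case for a change is that a primary decision rule should give the right answer without inference. A two-sided p-value has no sign, no readable passage defines percent change, and both terms are in use. Taken literally, the rule doubles the limiting error from 0.025 to 0.050. The repair would be a few words before unblinding, at no cost in model, alpha or power.

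Part of this stands. The readable wording is loose: on the usual sign convention the label and the inequality do not match, and the rejection sentence does not repeat the direction. The doubling, however, belongs to a reading that drops the hypotheses the sentence refers to. It is not an operating characteristic of the planned test. Two-sided p-values for a directional superiority claim are routine, and protocol 8.1.4 requires two-sided tests. The redacted SAP text and the unavailable shells may also state the sign or the direction, so the plan cannot be said to lack them.

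**Conclusion.** No change to the plan is needed. This is a slip of labelling and an abbreviated rule that any analyst would resolve in the same way: effective treatment means a larger percent reduction, and superiority requires both differences to favour the active. Read so, the test is valid at one-sided 0.025 for each lesion type. The effect on p-values, the equivalence interval and power for a true benefit is nil.

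The figures of 0.050 against 0.025 and 0.170 against 0.0015 apply only if the p-value sentence is used in isolation. They also rest on the normal model and on assumed standardised effects; the all-null and power figures depend in addition on the assumed splits of the block of seven. The label mismatch itself assumes that percent change is signed as Week 12 minus baseline. Restating the direction or renaming the variable would be an editorial nicety and would alter no result or correctly read conclusion.
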